5.3 Safety Evaluations

Evaluations include: adverse event reporting and physician evaluation. Adverse event reporting and physician evaluation will occur at every visit, if applicable. Telephone interview will occur on days 3, 15, and early termination (if applicable). Physical examination will occur at Screening, days 8, 29, 84, and early termination (if applicable).

6 SUBJECT SELECTION

6.1 Study Population

Subjects with a diagnosis of AK who meet the inclusion and exclusion criteria will be eligible for participation in this study.

6.2 Inclusion Criteria

- Adults at least 18 years old.
- Subjects must be able to read, sign, and understand the informed consent
- Subjects have at least 4 and no more than 20 clinically typical, visible actinic keratoses in the target treatment area on the face or scalp.
- Subject must be willing to forego any other treatments for AK in the treatment area on the face or scalp, during the study period, and for 14 days prior to enrollment; including cryotherapy, topical 5-fluorouracil, imiquimod, and ingenol mebutate.
- Subjects who have previously received PDT must undergo at least an 8-week washout period prior to enrollment in study.
- Subject must be willing and able to participate in the study and to comply with all study requirements including concomitant medication and other treatment restrictions, and telephone interview.
- If subject is a female of childbearing potential she must have a negative urine pregnancy test result prior to study treatment initiation and must agree to use an approved method of birth control while enrolled in the study. Women who are pregnant, lactating, or planning to become pregnant during the study period are excluded from the study.

6.3 Exclusion Criteria

- Subjects with any dermatologic disease in the treatment area that may be exacerbated by the treatment proposed or that might impair the evaluation of AKs.
- Subjects who are currently participating in another clinical study or have completed another clinical study with an investigational drug or device on the study area within 30 days prior to study treatment initiation.

- Subjects with any medical condition that in the opinion of the investigator, makes the patient unsuitable for the trial.

7 CONCURRENT MEDICATIONS

All subjects should be maintained on the same medications throughout the entire study period, as medically feasible, with no introduction of new chronic therapies.

7.1 Allowed Medications and Treatments

Bland topical emollients such as Eucerin and Cetaphil are allowed.

7.2 Prohibited Medications and Treatments

The following medications are prohibited during the study and administration will be considered a protocol violation: any topical prescription medication on the treatment area during the study.

8 STUDY TREATMENTS

8.1 Method of Assigning Subjects to Treatment Groups

Thirty eligible patients will be randomly assigned to one of three treatment arms (Conventional Arm, Combination Arm, Daylight Arm) in a 1:1:1 ratio using a SAS-based computer-generated randomization scheme developed by the study data management provider. The investigator or designee will complete a randomization worksheet prior to Visit 1.

8.2 Blinding

This is a single-blinded study, as the subject cannot be blinded to treatment. AK counts, local skin reaction, and ALA application will be performed by the blinded investigator. History, concomitant medications, randomization, light exposure, symptom assessment, and Skindex-16 will be administered by the unblinded study coordinator.

8.3 Formulation of Test and Control Products

8.3.1 Formulation of Test Product

The active study product is Aminolevulinic acid HCl topical solution 20% (Levulan Kerastick), developed by Sun Pharmaceutical Industries Ltd for topical administration in the management of minimally to moderately-thick AK of the face or scalp. Levulan Kerastick consists of a plastic tube containing two sealed glass ampules and a dry applicator tip. One ampule contains 354 mg ALA HCl as a dry solid, and the other ampule holds 1.5 mL of solution vehicle containing alcohol USP (ethanol content = 48% v/v), water, laureth-4, isopropyl alcohol, and polyethylene glycol. Levulan Kerastick 20% topical solution is obtained by breaking both ampules and shaking the plastic tube to mix contents.

8.3.2 Formulation of Control Product

Not applicable.

8.3.3 Packaging and Labeling

Aminolevulinic acid HCl topical solution 20% (Levulan Kerastick) is supplied in packages of six single-use plastic tubes with applicator tips. Each plastic tube contains one ampule of 354 mg ALA HCl as a dry solid and one ampule of 1.5 mL of solution vehicle.

Each carton (kit) of ALA HCl topical solution 20% will be labeled with the required FDA warning statement, the protocol number, the name of the investigator, patient number, name of sponsor, and directions for use and storage. Each tube will be labeled with the expiration date.

8.4 Supply of Study Drug at the Site

Sun Pharmaceutical Industries Ltd will ship ALA HCl topical solution 20% (Levulan Kerastick) to the investigational site. The initial Levulan Kerastick shipment will be shipped after site activation (i.e., all required regulatory documentation has been received by Sun Pharmaceutical Industries Ltd and a contract has been executed.) Subsequent Levulan Kerastick shipments will be made after site request for resupply.

8.4.1 Dosage/Dosage Regimen

Aminolevulinic acid HCl topical solution 20% (Levulan Kerastick) will be applied topically once by a healthcare provider on the day of treatment. One Levulan Kerastick will be applied to the treatment area on the face or scalp. Care will be taken to avoid the eyes and mouth.

Treatment arms are as follows:

- A. Conventional arm:** Acetone preparation, ALA topical application, 1 hour incubation, 16:40 BLU-U exposure, application of sunscreen.
- B. Combination arm:** Acetone preparation, ALA topical application, 15 minute incubation, 16:40 BLU-U exposure, application of sunscreen, 45 minute daylight exposure.
- C. Daylight arm:** Acetone preparation, ALA topical application, 15 minute incubation, application of sunscreen, 1 hour daylight exposure.

Due to photosensitivity, subjects should avoid sunlight, tanning beds, and any prolonged or intense light exposure for 40 hours after application of ALA HCl, outside of the assigned treatment regimen. Subjects should not wash or clean their faces until all steps of treatment have been completed.

8.4.2 Dispensing

The investigator or other training study staff will dispense ALA HCl 20% topical solution to be used by the study provider on treatment day. Medication will not be dispensed to the subjects for home use.

8.4.3 Administration Instructions

Aminolevulinic acid HCl 20% topical solution (Levulan Kerastick) will be applied topically once by the study provider. After acetone preparation of the treatment area,

Levulan Kerastick will be applied to the subject's affected areas within the treatment area. The treatment area will be either the face or scalp; the site will be determined at Screening. Prior to Levulan treatment, any hypertrophic AKs in the treatment area will be scraped with a curette by the study provider to remove thick scale.

The study provider will prepare and administer Levulan Kerastick in the following manner:

1. Hold Levulan Kerastick so the applicator cap is pointing up.
2. Crush bottom ampule containing solution vehicle by applying finger pressure to marked location on the cardboard sleeve.
3. Crush the top ampule containing the ALA HCl powder by applying finger pressure to marked location on the cardboard sleeve. To ensure both ampules are crushed, continue crushing the applicator downward.
4. Holding the Levulan Kerastick between the thumb and forefinger, pointing the applicator cap away from the face, shake the Levulan Kerastick gently for at least 30 seconds to mix ALA HCl and solution vehicle. Do not press on end cap while shaking.
5. Apply contents of one Levulan Kerastick using applicator tip to all affected areas within treatment area. Mouth, periorbital area, and all mucosal surfaces will be avoided.

Depending on the assigned treatment arm, patients will receive 16 minutes, 40 seconds of artificial blue light on the treatment area via BLU-U blue light phototherapy illuminator and/or daylight exposure for the assigned duration. Light exposure will be provided by the unblinded study provider.

8.4.4 Storage

Study drug should be stored by the study site at controlled room temperature, 15 to 30°C (59-86°F). If the temperature of study drug storage in the clinic/pharmacy exceeds or falls below this range, this should be reported to the designee and captured as a deviation.

8.5 Study Drug Accountability

An accurate and current accounting of the dispensing of study drug for each subject will be maintained on an ongoing basis by a member of the study site staff.

The number of study drug dispensed for each subject will be recorded on the Investigational Drug Accountability Record.

8.6 Measures of Treatment Compliance

Not applicable.

9 STUDY PROCEDURES AND GUIDELINES

A Schedule of Events representing the required testing procedures to be performed for the duration of the study is diagrammed in Appendix 1.

Prior to conducting any study-related activities, written informed consent and the Health Insurance Portability and Accountability Act (HIPAA) authorization must be signed and dated by the subject or subject's legal representative. If appropriate, assent must also be obtained prior to conducting any study-related activities.

9.1 Clinical Assessments

9.1.1 Concomitant Medications

All concomitant medication and concurrent therapies will be documented at Baseline/Screening and at Study Days 1 (may be combined with screening), 8, 29, 84, and at early termination when applicable. Dose, route, unit frequency of administration, and indication for administration and dates of medication will be captured.

9.1.2 Demographics

Demographic information (date of birth, gender, race) will be recorded at Screening.

9.1.3 Medical History

Relevant medical history, including history of current disease, other pertinent respiratory history, and information regarding underlying diseases will be recorded at Screening.

9.1.4 Physical Examination

A complete physical examination will be performed by either the investigator or a subinvestigator who is a physician at Screening. Qualified staff (MD, NP, RN, and PA) may complete the abbreviated physical exam at all other visits. New abnormal physical exam findings must be documented and will be followed by a physician or other qualified staff at the next scheduled visit.

9.1.5 Vital Signs

Body temperature, blood pressure, pulse and respirations will be performed after resting for 5 minutes at Screening and at day 1.

9.1.6 Actinic keratosis (AK) count

An AK count will be performed to count the lesions in the treatment area. AK count will be performed at Screening and at days 1, 8, 29, and 84.

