5.2 Secondary Efficacy Endpoints

The secondary efficacy endpoints are efficacy, local skin reaction to treatment, and symptoms and local skin response during follow-up period.

- 1) Efficacy in clearance of AK at 12 weeks:
 - A. percent reduction in number of AKs from baseline to 12 weeks
 - B. proportion of subjects with complete and partial clearance of AKs as described above.
- 2) To determine whether daylight PDT affords, at end of treatment, a reduction in composite local skin reaction

- 3) To determine whether daylight PDT has a faster resolution of composite treatment symptoms and local skin response during days 8, 29, and 84.

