9.1.7 Local Skin Reaction (LSR)

Local skin reaction based on known response to PDT (Levulan package insert) will be graded by visual assessment on a custom 4 point scale where 0=none, 1=mild, 2=moderate, 3=severe. Each of the following four reactions will be graded: erythema, vesiculation/postulation, crusting/scabbing/erosion, and edema/swelling. A composite

score will be calculated (range 0-16). LSR assessment will be performed at days 1, 8, 29, and 84.

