10 EVALUATIONS BY VISIT

All study visits will have a window +/- 3 days.

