10.8 Early Withdrawal Visit

Unblinded investigator:

1. Record changes to concomitant medications.
2. Perform complete physical examination.
3. Record any Adverse Events.
4. Symptom assessment
5. Record Skindex-16
6. Photography of treatment area.

Blinded investigator:

7. Perform AK count
8. Record LSR

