12 DISCONTINUATION AND REPLACEMENT OF SUBJECTS

12.1 Early Discontinuation of Study Drug

A subject may be discontinued from study treatment at any time if the subject or the investigator, or the Sponsor feels that it is not in the subject's best interest to continue. The following is a list of possible reasons for study treatment discontinuation:

Subject withdrawal of consent (or assent)

Subject is not compliant with study procedures

Adverse event that in the opinion of the investigator would be in the best interest of the subject to discontinue study treatment

Protocol violation requiring discontinuation of study treatment

Lost to follow-up

Sponsor request for early termination of study

Positive pregnancy test (females)

If a subject is withdrawn from treatment due to an adverse event, the subject will be followed and treated by the Investigator until the abnormal parameter or symptom has resolved or stabilized.

All subjects who discontinue study treatment should come in for an early discontinuation visit as soon as possible and then should be encouraged to complete all remaining scheduled visits and procedures.

All subjects are free to withdraw from participation at any time, for any reason, specified or unspecified, and without prejudice.

Reasonable attempts will be made by the investigator to provide a reason for subject withdrawals. The reason for the subject's withdrawal from the study will be specified in the subject's source documents Refer to Section 10 for early termination procedures.

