15.4 Analysis of Secondary Endpoints

Efficacy and tolerability data will be summarized by each secondary endpoint.

Symptom level over time during the treatment period will be graphed for visualization along the three axes of pain, stinging/burning, and itching/pruritus as well as a composite symptom score. Peak symptom level during the treatment period and pain at the end of treatment exposure will be compared between the conventional treatment arm (A), the combination treatment arm B), and the daylight treatment arm (C), with unpaired t-tests.

Percent reduction in the number of actinic keratoses and proportions of patients with partial and complete clearance of actinic keratoses will be presented descriptively and visualized as histograms. We will compare the percent reduction in the number of AKs and the proportions of patients with clearance between the conventional treatment arm (A) and the combination treatment arm B), and between the conventional treatment arm (A) and the daylight treatment arm (C), using unpaired t-tests.

All analyses will be based on the intent-to-treat (ITT) population. In the ITT population, patients will be counted in the treatment group upon randomization, regardless of receiving any dose of study medication. For efficacy analysis, all missing values due to patient early termination from the study will be imputed using last observation carried forward (LOCF) method, as appropriate. For each patient, the Baseline values will be defined as those values recorded at Day 1 prior to dosing. Patients who are lost-to-follow-up after Baseline will be included to the ITT population carrying forward their Baseline values.

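### No rule limits which AK count may be carried to 12 weeks, so a count from about one week after treatment can become the clearance result, while the next sentence would carry Baseline instead

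*Combined protocol and SAP*

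**What the plan says.** The efficacy endpoints in section 5.2 are "percent reduction in number of AKs from baseline to 12 weeks" and the proportions of subjects with complete and partial clearance at that time. No AK endpoint is defined at an earlier visit.

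Counts are nevertheless taken earlier. Section 9.1.6 states: "AK count will be performed at Screening and at days 1, 8, 29, and 84". Section 10 adds: "All study visits will have a window +/- 3 days". The early withdrawal visit in section 10.8 includes the item "Perform AK count", with no minimum interval from treatment. Section 12.1 says that subjects who stop "should come in for an early discontinuation visit as soon as possible", and then asks that they be encouraged to complete the remaining visits.

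For missing data, section 15.4 (and the synopsis) says that for efficacy "all missing values due to patient early termination from the study will be imputed using last observation carried forward (LOCF) method, as appropriate". The paragraph ends with a second rule, under which subjects lost to follow-up after Baseline stay in the ITT population with their Baseline values. Neither sentence says which post-treatment AK counts may be carried, or which rule governs a subject who has a Day 8 count and is then lost.

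**The concern.** The Day 8 count is not an endpoint. Its only route into a planned efficacy comparison is imputation for a subject who has no later count, and the same is true of a withdrawal count made soon after treatment. A count at about one week answers a different question from clearance at 12 weeks, however well it is made.

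It may also be harder to make. Section 5.2 treats Day 8 as part of the period over which the skin response resolves, so the plan expects that some reaction may still be present. The grades in Appendix V place scale, crust, swelling and erosion on individual lesions, which is where the AKs are counted. Under section 10.2, hypertrophic AKs are curetted after the Day 1 count, so some baseline lesions may have been scraped about a week before. Crust could hide an AK, or an inflamed site could be counted as one.

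At stake is the comparison of AK reduction and clearance between the conventional arm and each of the other two arms. With 10 subjects per arm, a single imputed value has visible weight.

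**Working it through.** **Plan's own figure.** There is none for AK clearance or dropout. The only design figure (section 15.6: 10 per group, 1.25 points, two-sided alpha 0.05, power 0.8) concerns pain, and this point does not depend on it.

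**Inputs from the documents.** 10 subjects per arm (4.1); no replacement (12.3); 4 to 20 AKs at entry (6.2); counts on Days 1, 8, 29 and 84 (9.1.6); window of 3 days either side (10).

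**Step 1: timing.** The Day 8 visit may fall from Day 8 - 3 = 5 to Day 8 + 3 = 11. The Day 29 window opens on Day 29 - 3 = 26. A withdrawal visit can fall on any day after treatment.

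**Step 2: the two sentences applied to one subject.** Take a subject with a Day 1 and a Day 8 count who leaves before Day 29 and does not return. Let r be the percent reduction at Day 8, where r = 100 x (Day 1 count - Day 8 count) / Day 1 count.

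| Rule in 15.4 | Value used at 12 weeks | Percent reduction | Clearance status |
|---|---|---|---|
| LOCF after early termination | Day 8 count | r | as seen on Day 8 |
| Baseline carried after loss to follow-up | Day 1 count | 0 | not cleared |

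The choice between the rules moves the arm mean by r/10: 25/10 = 2.5 points, 50/10 = 5 points, 100/10 = 10 points. If the Day 8 count shows clearance, the choice also moves the arm's clearance rate by 1/10 = 10 points.

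**Step 3: effect of a carried count that misstates the 12-week result.** For k such subjects, each wrong by d points, the arm mean shifts by k x d / 10. The values of k and d are assumed.

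- k = 1: d = 25 gives 2.5 points; d = 75 gives 7.5 points.
- k = 2: d = 25 gives 5 points; d = 75 gives 15 points.
- One wrong clearance status gives 10 points; two give 20.

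For scale, one miscounted lesion is 100/4 = 25 points of a subject's percent reduction at a baseline of 4 AKs, and 100/20 = 5 points at a baseline of 20.

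**Step 4: how often.** The documents give no dropout rate. If a proportion p leaves between Day 8 and Day 29, the chance that at least one of n subjects does so is 1 - (1 - p)^n.

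| Assumed p | At least one of 30 | At least one in an arm of 10 |
|---|---|---|
| 2% | 45% | 18% |
| 5% | 79% | 40% |
| 10% | 96% | 65% |

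These are illustrations. A subject who leaves but returns for Day 84 has an observed value, and nothing is carried.

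**The case against.** Several stronger readings are tempting, and the documents do not support them.

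- *The plan itself says that the reaction spoils the count.* It does not. The phrase "that might impair the evaluation of AKs" in section 6.3 is about skin disease as a reason for exclusion, not about the reaction to treatment. Section 2.1 lists crusting and erosion among reactions in more than 10% of patients and says that reactions typically begin on day 1, but gives no duration. Impaired counting on Day 8 is a reasonable inference and no more.
- *Grading skin reaction at the same visit shows an acute phase.* It does not, because "LSR assessment will be performed at days 1, 8, 29, and 84", which includes the endpoint visit itself.
- *Every early-withdrawal count is affected.* Withdrawal can occur at any time before Visit 7. A count made weeks after Day 29 need not fall in an acute phase, and section 12.1 encourages subjects who stop to complete the remaining visits.
- *LOCF always makes the early count the result.* The LOCF sentence ends with an undefined qualifier, and the Baseline sentence may override it. But neither of these bars the early count. They leave the value open, which is itself a defect.
- *The bias favours a known arm.* Whether skin reaction differs by arm is a question the trial asks (section 3.2). Error can run either way, so neither its direction nor its difference between arms follows.

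It is also fair to say that this is a secondary endpoint in a study that calls itself small and descriptive, and that section 15 promises a fuller SAP. Both points lower the severity. The second also means that the correction is easy to make.

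**Conclusion.** The concern holds in a limited form. The plan does not restrict which AK count may be carried to 12 weeks, and two sentences in one paragraph give different values for the same subject. As a result, a count from about one week after treatment, or from an early withdrawal visit, can serve as the 12-week result for a subject who leaves before Day 29 and does not come back. The mismatch in timing is enough to make this a poor rule. Possible obscuring of lesions adds to it but is inferred.

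Each affected subject whose clearance status is wrong moves that arm's rate by 10 points, and a misstatement of 25 to 75 points of percent reduction moves the arm mean by 2.5 to 7.5 points. The number of such subjects and the size of the error are assumptions. Taking a count on Day 8 is not a flaw in itself. Severity is minor to moderate.

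**What to change.** In section 15.4 and the synopsis, replace the two imputation sentences, as they apply to AK counts, with one rule:

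1. No post-treatment AK count taken before the Day 29 visit window is carried to Day 84.
2. For complete and partial clearance, a subject with no count from the Day 29 window onward is classified as not cleared.
3. For percent reduction, use one stated method that keeps all randomised subjects, for example the Baseline value (0% reduction) for a subject with no count from the Day 29 window onward.
4. As sensitivity analyses, report observed cases and a mixed model of the Day 29 and Day 84 counts with the Day 1 count as covariate. The model suits a sensitivity role because subjects with neither count contribute no outcome to it.

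The Day 8 count can stay in section 9.1.6, section 10.4 and Appendix I, labelled as descriptive only.

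The cost is wording; no visit or assessment is added. The downside is that subjects lost before Day 29 count as not cleared. That is conservative, and each such subject can move the arm's rate by up to 10 points, which is why the observed-case result should be shown beside it.
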